## **13. STATISTICAL METHODS/DATA ANALYSIS**

### **13.1 Study endpoint**

For assessment of normally distributed parameters the Shapiro-Wilk method will be used. Student's t-test will then be applied for both paired and unpaired samples. Between-group differences at one time point will be evaluated by Wilcoxon-Mann-Whitney test (continuous variables) and Fisher's Exact test (categorical variables). Data analysis will be performed using Stata SE, version 12.1. All statistical tests will be two-sided and statistical significance level alpha will be set at 0.05 for the analysis.

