**Study Population**

Newly diagnosed and confirmed patients with NASH, males and females, aged from 40-65 years.

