**Study Design**

The study is designed as a double-blinded, interventional, randomized clinical study involving patients with NASH. A major research question is whether ingestion of lycopene stabilized with Lycosome™ formulated phosphatidylcholine chaperone can reverse clinical and laboratory manifestations of NASH. Therefore, the primary endpoint of the project is the size of the liver and parameters reflecting lipid accumulation in the hepatic tissue at the end of the interventional period. Changes in the activity of liver-specific enzymes and parameters of lipid homeostasis represent the secondary question since normalization of serum levels of hepatic enzymes represents another important criterion of liver damage and its reversal in NASH. Biochemical parameters in serum specimens will be investigated before commencing the study, at the intermediate time points of 1 month and in the end of the study after 2 months treatment. To assess changed in the liver span Ultrasonography was used before and in the end of the trial.

Subjects will be assigned to take orally once a day either capsules containing 450 mg of regular phosphatidylcholine or 450 mg of the same phospholipid in Lycosome™ formulation with 7 mg of lycopene (Cambridge, UK).

The formulations will be dispensed to the subjects during follow-up visits each month. Monthly visits are planned to determine compliance and adherence to the protocol. A basic medical check-up will be performed and subjects will be asked questions to determine adherence to the protocol during each visit.

Packaging and labeling of the study products will be carried out according to the guidelines of NIH and US Department of Health and Human Services as recommended for biologics and investigational health food products. The formulations will be shipped to the study site in specially designed containers with primary and secondary components. The container closure system will prevent exposure of the investigational products to light, moisture, temperature extremes and air. This packaging system guarantees stability of the product for intended use. Protection from microbial contamination will be provided by maintaining container integrity after the packaging system is sealed. An adequate and validated procedure was used for investigational product manufacture and packaging.

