**7. CLINICAL PROTOCOL****7.1 Introduction****Background**

Lycopene is a polycarbon polyunsaturated red pigment from certain fruits and vegetables (tomatoes, papaya, strawberries, red bell pepper and cherries) which belongs to the carotenoid family and has extremely powerful antioxidant properties in vivo and in vitro (1). There is a growing body of clinical evidence that introduction of lycopene into the human diet prevents multiple diseases such as prostate cancer, type 2 diabetes and atherosclerosis. Recent studies indicate that lycopene supplementation deeply affects liver functions (2). In particular, as shown under experimental conditions, lycopene can prevent development of steatohepatitis in rodents (3).

Steatohepatitis, otherwise known as fatty liver disease, is a common pathological condition of liver which is characterized by accumulation of lipids in the hepatic tissue (4). Steatohepatitis accompanies multiple internal diseases such as obesity, type 2 diabetes, insulin resistance and hyperlipidemia and may finally result in liver cirrhosis (5). Although the exact number of patients with steatohepatitis in the world is not precisely defined, this number may approach 250 million patients who suffer from obesity and type 2 diabetes (6). Methods for steatohepatitis treatment are not well defined or standardized as yet. Diet, exercise and antiglycemic drugs are believed to be helpful in management of steatohepatitis, however no specific medication has been proposed as yet (7).

However, there is recent evidence that vitamin E therapy may attenuate steatohepatitis development (8). This suggests that use of antioxidants, including lycopene, may represent a novel strategy in treatment of steatohepatitis (8).

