## **10. CONCOMITANT MEDICATIONS**

Patients with concomitant intake of anti-hypertensive, lipid-lowering or any other cardio-vascular drugs will be illegible for the study. Subjects will be allowed to take prescription medication assigned by primary care physician.

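### Section 13.1 plans within-arm before-after t-tests next to between-group tests without saying which decides the primary question, so an uncontrolled change could be reported as reversal of NASH

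*Protocol*

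**What the plan says.** The Study Design section of the Protocol Summary describes a double-blind randomised trial with two groups. Its major question is whether lycopene with the phosphatidylcholine chaperone "can reverse clinical and laboratory manifestations of NASH". No comparator appears in that sentence. The section then states that "the primary endpoint of the project is the size of the liver", together with measures of hepatic lipid, at the end of the interventional period. Liver span is measured before and at the end of the trial.

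Section 13.1, headed Study endpoint, fixes the tests. After a Shapiro-Wilk check, Student's "t-test will then be applied for both paired and unpaired samples". A separate sentence covers the randomised comparison: "Between-group differences at one time point will be evaluated by Wilcoxon-Mann-Whitney test (continuous variables"), with Fisher's exact test for categorical data. On error rates: "All statistical tests will be two-sided and statistical significance level alpha will be set at 0.05 for the analysis". No test is tied to a named endpoint, and none is called primary or descriptive.

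Four other places bear on how a before-after change would be read:

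- Study Population: "Newly diagnosed and confirmed patients with NASH".
- Section 7.1: "Diet, exercise and antiglycemic drugs are believed to be helpful in management of steatohepatitis".
- Section 10: "Subjects will be allowed to take prescription medication assigned by primary care physician".
- Section 7.3, secondary objectives: one objective is the effect of the phosphatidylcholine chaperone by itself, although both arms receive phosphatidylcholine.

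**The concern.** A paired test in the lycopene arm asks whether the mean changed between two visits. It does not ask why. Several things other than the product could move liver size, enzymes or lipids after Day 0:

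- Patients qualify on abnormal CT and laboratory results, which invites some regression to the mean.
- Diabetes with HbA1c up to 11% is admitted, and primary-care prescriptions may continue or start during the trial.
- The protocol regards diet, exercise and glucose-lowering drugs as helpful, and no section holds them constant.

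Randomisation deals with all of this, but only in a comparison between arms. Because the research question is worded as reversal, and the paired tests carry the same 0.05 threshold with no lower rank, the protocol leaves room to report a significant before-after change in the lycopene arm as an answer to the main question, even if the arms do not differ. What is at stake is the attribution of the change. The paired test may be quite right that the mean moved.

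**Working it through.** **The plan's own figure.** Section 13.2 gives 80 patients (40 per group) at one-sided 2.5% and 90% power; the Protocol Summary gives 40 patients (20 per group). Neither can be reproduced, because no difference or SD is stated. Solving d = (1.960 + 1.282) × √(2/n) gives an implied standardised difference of 0.725 at 40 per arm and 1.025 at 20 per arm. The present point does not depend on either value. Both sizes are carried below because the document does not settle between them.

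**Meaning of paired.** The trial has two parallel arms, with liver size measured before and after, and describes no matched pairs of patients. A paired t-test is therefore a one-sample t-test on change scores within an arm.

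**Inputs.** n = 20 or 40 per arm; two-sided alpha 0.05 (Section 13.1); product effect set to zero. The background change m, common to both arms and in units of the SD of the change score, is an assumption, shown for 0.2, 0.3 and 0.5.

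**Formula.** With noncentrality m√n and n − 1 degrees of freedom, P(significant) = P(|T| > t₀.₉₇₅), where T is noncentral t. The critical values are 2.093 (n = 20) and 2.023 (n = 40).

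| n per arm | m (assumed) | m√n | Paired test in lycopene arm significant | Between-arm t-test on change significant |
|---|---|---|---|---|
| 20 | 0.2 | 0.894 | 14% | 5% |
| 20 | 0.3 | 1.342 | 25% | 5% |
| 20 | 0.5 | 2.236 | 56% | 5% |
| 40 | 0.2 | 1.265 | 23% | 5% |
| 40 | 0.3 | 1.897 | 46% | 5% |
| 40 | 0.5 | 3.162 | 87% | 5% |

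The last column is constant because m is the same in both arms and cancels in the difference. A simulation of 100,000 trials per scenario confirmed both columns. With m = 0, the paired test also returns 5%.

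**A related misreading.** The pattern of significant improvement in the lycopene arm and none in the control arm also arises without any product effect. If p is the chance that one arm shows significant improvement, the pattern has probability p(1 − p), because the arms are independent. For n = 20 and m = 0.5 this is 0.5645 × 0.4355 = 0.246. For n = 40 and m = 0.3 it is 0.4565 × 0.5435 = 0.248. The ceiling is 25%.

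**The case against.** The strongest reply is that the valid comparison is already planned. Section 13.1 gives between-group differences at one time point their own sentence, and that fits a primary endpoint defined at the end of the interventional period. The order of tests is often left to a statistical analysis plan, which may exist. Paired tests also have a legitimate use here, since only a before-after comparison can address the objective on phosphatidylcholine by itself.

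Much of this stands. A reader might infer that the major question is reversal within the lycopene arm and that the paired test is its designated test. The documents do not say so: the question follows directly on the description of a randomised two-group study, and no section assigns the paired test to it.

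A reader might also infer that both arms will probably improve, so that a significant paired result with no difference between arms is the likely outcome. That is not supported either:

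- No section gives a size for background change, and in four of the six scenarios above the paired test is significant less than half the time.
- Newly diagnosed appears only in the Study Population summary. The inclusion criteria ask for CT and laboratory results within 90 days before randomisation.
- Sections 7.4.1 and 7.4.2 provide for re-screening after a wash-out and a fresh Day 0 baseline, which should reduce regression to the mean.
- Section 10 is unclear about patients on lipid-lowering and other cardiovascular drugs: the word used there is plausibly a slip for ineligible. It cannot firmly support an expected fall in lipids.

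Finally, a paired test that rejects when the mean has truly changed is not a false positive about change. The error would lie in attributing the change to the product.

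What the reply does not remove is that the protocol itself fixes an uncontrolled test and a controlled test at the same threshold, ranks neither, and words its main question so that either could seem to answer it. That goes beyond detail left to a later plan.

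**Conclusion.** The point holds as a weakness in what the protocol fixes, and should be corrected. It does not invalidate the design, because the randomised comparison is available and is planned. Under the assumed background changes of 0.2 to 0.5 SD, the lycopene-arm paired test would be significant in 14% to 56% of trials at 20 per arm and 23% to 87% at 40 per arm without any product effect, against 5% for the between-arm test of change. These figures rest on normally distributed change scores and the same background change in both arms. They show how far a paired result could mislead; they do not forecast this trial. The qualitative conclusion needs no figure: a within-arm change cannot identify a product effect.

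**What to change.** 1. In Section 13.1, make the between-arm difference in change from Day 0 in liver size, or in the final value adjusted for baseline, the sole basis for the efficacy conclusion.
2. In the same section, label paired within-arm tests as descriptive.
3. In the Study Design section, word the major question as improvement relative to the phosphatidylcholine control.
4. In the secondary objectives of Section 7.3, state that the objective on phosphatidylcholine by itself is descriptive, because the design has no arm without phosphatidylcholine.

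Notes on diet or exercise advice and new prescriptions at the existing visits, reported by arm, would help interpretation. They are optional and the point does not depend on them.

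The cost is wording in three sections, with no added patients or visits. The real downside is that the sponsor gives up a before-after efficacy claim.

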## **7.4 Study Design**

### **7.4.1 Selection and randomization of volunteers**

Medical personnel from the outpatient clinic of the Institute of Cardiology, Saratov, Russian Federation will be informed about launching the study, its major goal and selection criteria for volunteers. Suitable individuals will be invited for a preliminary check-up (physical and laboratory investigation) during the initial phase of enrolment. All suitable individuals will be re-screened after the wash-out period of the study before the final decision on study enrolment is made.

Randomization of volunteers in the study will be performed using widely accepted methods such as simple randomization and stratified randomization. Briefly, software containing a random number generator will be applied to the database of volunteers. The assigned group will be considered final. The groups will be balanced according to numerical age and gender with special software.

Stratified randomization will be used to enhance the statistical power of the final results and will ensure equality of groups for secondary selection criteria.

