### **13.3 Statistical effectiveness analysis**

Statistical analysis of results will be performed by an independent statistician. If the statistical methods and settings listed above are not appropriate for the newly obtained results due to specificity of variant distribution, other methods of statistical analysis will be applied. Any deviations from the statistical plan described above will be explained and justified in a protocol amendment and/or in the final report submitted to the Institutional Ethics Committee.

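### Section 13.1 leaves the deciding between-group test unfixed and makes no use of baseline, age or gender; the tests are valid, but precision is given away

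*Protocol*

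**What the plan says.** Protocol section 13.1 gives the rules for continuous variables in three sentences. The first is "For assessment of normally distributed parameters the Shapiro-Wilk method will be used". The second is "Student's t-test will then be applied for both paired and unpaired samples". The third is "Between-group differences at one time point will be evaluated by Wilcoxon-Mann-Whitney test (continuous variables"). All tests are two-sided at 0.05.

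Section 13.3 adds that if the listed methods do not suit the results obtained, "due to specificity of variant distribution, other methods of statistical analysis will be applied". Deviations must be explained and justified, either in an amendment or in the final report. The analysis is given to an independent statistician. The Study Design text in section 6 has an independent statistician hired at the end of the study to break the code.

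On the data available, section 7.4.2 schedules clinical and laboratory measurements and computed tomography on Day 0. On allocation, section 7.4.1 says "The groups will be balanced according to numerical age and gender with special software" and, separately, "Stratified randomization will be used to enhance the statistical power of the final results".

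**The concern.** There are two problems.

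**The analysis does not use what the design collects.** Every subject has a Day 0 value, and the groups are balanced on age and gender. The only between-group methods named are two-sample tests with no covariates. Paired t-tests do use baseline, but only within an arm, so they do not answer the randomised question. Liver size and enzyme levels can be expected to vary between people and to track within a person. Where they do, leaving baseline out costs power. Balancing on a prognostic factor and then omitting it from the test also forgoes much of the power gain that section 7.4.1 claims for stratification.

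**The deciding test is not fixed.** Both a t-test and a Wilcoxon test are named for the same unpaired contrast, with no rule for which governs. Section 13.3 then lets unnamed methods replace both after the results are in. A reader of the final report could not tell whether the test was chosen before or after the answer was known.

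**Working it through.** **Reference effect.** Section 13.2 states one-sided 2.5%, 90% power and 40 per group, but no difference or SD, so that sample size can be neither reproduced nor refuted. One-sided 2.5% has the same critical value as two-sided 5%. Solving backwards:

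d = (1.960 + 1.2816) × √(2/40) = 0.725 SD.

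Section 6 gives 20 per group instead. That conflict is a separate matter, so both sizes are shown.

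**Assumption.** The correlation r between baseline and final value is not in the protocol. I take 0.3, 0.5 and 0.7.

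**Power** (non-central t, two-sided 5%, n per group), with non-centrality (0.725/s) × √(n/2):

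- final value, unadjusted t-test: s = 1, 2n − 2 degrees of freedom
- change from baseline: s = √(2(1 − r)), 2n − 2 degrees of freedom
- ANCOVA on baseline: s = √(1 − r²), 2n − 3 degrees of freedom

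Example at n = 20, r = 0.5. Unadjusted: 0.725 × √10 = 2.29, power 61%. ANCOVA: (0.725/0.866) × √10 = 2.65, power 73%.

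| n per group | r | Unadjusted t | Change score | ANCOVA |
|---|---|---|---|---|
| 40 | 0.3 | 89% | 77% | 92% |
| 40 | 0.5 | 89% | 89% | 96% |
| 40 | 0.7 | 89% | 99% | 99% |
| 20 | 0.3 | 61% | 47% | 65% |
| 20 | 0.5 | 61% | 61% | 73% |
| 20 | 0.7 | 61% | 82% | 88% |

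Because 1 − r² = (1 − r)(1 + r) never exceeds 2(1 − r), the ANCOVA SD is never larger than the change-score SD. Simulation with normal data (8,000 trials per setting, r = 0.5 and 0.7) put the unadjusted Wilcoxon test at 58–59% with 20 per group and 87–88% with 40. The corresponding ANCOVA figures were 73% and 86% with 20 per group, and 95% and 99% with 40.

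In sample-size terms, ANCOVA needs 40 × (1 − r²) per group for the same 90% power: 37, 30 and 21 after rounding up.

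**Omitted balancing factors.** If the balanced factors explain a share R² of the variance (also assumed), the unadjusted standard error is too large by about 1/√(1 − R²). The actual type I error is then about 2 × [1 − Φ(1.96/√(1 − R²))]. For R² = 5%, 10%, 20% and 30% this gives 4.4%, 3.9%, 2.8% and 1.9%.

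**Choice between the two tests.** In the same simulations under no effect, each single unadjusted test stayed near 5% (4.7–5.3%). Using the t-test when Shapiro-Wilk passes and Wilcoxon otherwise gave 5.2–5.4%. Taking the smaller of the two p-values gave about 6%.

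**The case against.** Several objections carry weight.

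- **The tests are valid.** An unadjusted Wilcoxon or t-test holds its type I error, or falls below it after balancing. This stands. A reader might infer that the analysis is invalid or that false positives are seriously inflated; the figures do not support that.
- **Section 13.1 can be read as an ordinary two-step rule**, with normality checked first, then t, otherwise Wilcoxon. On that reading the type I error is barely above 5%. The 6% figure needs the smaller p-value to be picked, which the protocol does not authorise. This stands, but the two-step rule is not actually written down.
- **Baseline may still enter through change scores.** Section 13.1 does not exclude them, and the Study Design text in section 6 speaks of changes in enzymes. So one cannot say that baselines are certainly ignored. The same text, however, places the primary endpoint at the end of the interventional period, and change scores remain less efficient than ANCOVA.
- **Age and gender may not be strata.** Section 7.4.1 mentions both simple and stratified randomisation, balances age and gender by software, and ties stratification to unnamed secondary criteria. Calling this age and gender stratification is an inference. The conservatism in the type I error depends on how tightly the groups are balanced and how prognostic the factors are, and it is small at 5–10% of variance explained.
- **Switching is not unrestricted.** Section 13.3 ties it to the distribution of the data and demands justification. It does not demand this before unblinding.
- **Adjustment is usually left to a SAP.** True in general, but here the protocol fixes the tests itself.

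**Conclusion.** The point holds as lost precision and an unfixed deciding test. At 0.725 SD, and over assumed correlations of 0.3 to 0.7, ANCOVA adds about 3 to 10 percentage points of power over the unadjusted t-test with 40 per group, and about 4 to 27 with 20 per group. The lower starting power at 20 per group comes from the smaller sample, not from the choice of test, so the larger gain should not be quoted alone. Change scores would recover part of the gain at a correlation of 0.7 and none at 0.5.

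Omitting balanced factors costs little if they explain 5% of the variance (type I error about 4.4%) and more at 30% (about 2%). Test selection adds at most about 1 percentage point to the type I error if the choice is between t and Wilcoxon only. The effect of the unnamed methods in section 13.3 cannot be bounded from the document. No correlation, variance share or effect size is given in the protocol, so the direction is firm and the size is conditional. The change should be made, because it improves the trial without new data.

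**What to change.** In section 13.1, make the between-group analysis of each continuous endpoint an ANCOVA of the final value on arm, baseline value, age and gender, plus any stratification factor actually used. Report the adjusted difference with its 95% confidence interval. A log scale may be used for skewed laboratory values if that is fixed before unblinding. Keep the Wilcoxon-Mann-Whitney test as a sensitivity analysis, drop Shapiro-Wilk as a gate, and label the within-arm paired tests as descriptive.

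In section 13.3, require any change of method to be documented, with reasons, before the code is broken.

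The cost is analysis wording and a few degrees of freedom. With 20 per group, baseline, age and gender take the residual degrees of freedom from 38 to 35. No new data or visits are needed. This does not settle which variable is primary; the sponsor has to name it separately.

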#### **7.4.2 Schedule of Procedures/Evaluations**

1. 2 months prior to study initiation. (Initial enrolment with preliminary physical and laboratory investigation).
2. 2 – 5 days prior to study initiation. Final qualifying physical and laboratory investigation.
3. Day "0" of the study. Physical and laboratory investigation to obtain baseline clinical and laboratory values. Computed tomography.
4. End of the 2nd and 4th months of the study. Physical and laboratory investigation to obtain mid-point clinical and laboratory values.
5. End of the 6th month of the study. Concluding physical and laboratory investigation to obtain final clinical and laboratory values. Computed tomography.

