## **12.2 Withdrawal of subjects due to adverse events**

Any subject with an adverse reaction and/or abnormal laboratory test findings will be withdrawn from the study by the Medical Officer and replaced with an eligible volunteer from the pre-screened pool of volunteers. An appropriate report to the Local Ethical Committee will be filed.

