### **13.2 Sample size determination**

Sample size has been determined based on preliminary results obtained in our previously published pilot clinical study and statistics obtained in our work.

Sample size has been calculated based on standard deviation values according to methods widely described elsewhere. The major statistical requirements will be pre-specified in our work as follows: significance of probability in one-tailed test will be taken to be 2.5%; the statistical power level will be chosen to be 90%.

With these requirements for sample size determination we decided to enroll a total of 80 volunteers (40 individuals per group).

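### Single-time-point tests of repeatedly measured enzymes and lipids leave out withdrawn subjects' mid-point values, which can dilute a real final-visit difference on these secondary endpoints

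*Protocol*

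**What the plan says.** **Tests.** Protocol section 13.1 checks normality and then says "Student's t-test will then be applied for both paired and unpaired samples". For comparisons between arms it says "Between-group differences at one time point will be evaluated by Wilcoxon-Mann-Whitney test (continuous variables". It does not name the time point. Section 13.3 lets other methods be used when the distribution of a variable makes the listed ones unsuitable. It does not extend this to missing values.

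**Visits.** Two schedules stand in the protocol.
- The summary (Study Design) takes serum biochemistry before the study and then "at the intermediate time points of 1 month and in the end of the study after 2 months treatment".
- Section 7.4.2 has Day 0, visits at months 2 and 4 ("Physical and laboratory investigation to obtain mid-point clinical and laboratory values") and a concluding visit at month 6.

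Under either schedule at least one laboratory value lies between Day 0 and the end. Section 11 also says that effectiveness is assessed at intermediate and final points.

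**Exit.** Section 12.2 says "Any subject with an adverse reaction and/or abnormal laboratory test findings will be withdrawn from the study by the Medical Officer", and that the subject is replaced. Section 17.1 replaces every withdrawn subject. Sections 9, 12 and 17.1 add exits for poor adherence, for rash, dyspepsia or nausea, and at the subject's request.

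**Status.** The summary makes enzymes and lipids the secondary question. Liver size and liver fat are primary.

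**The concern.** The protocol ties withdrawal to laboratory results obtained after randomisation, and the same kind of result is a secondary endpoint. It then names tests that see one visit at a time. A subject withdrawn after an intermediate visit has a recorded value that helps to explain the exit, but that value plays no part in a final-visit comparison.

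If the product lowers enzymes, more control than active subjects will cross any fixed limit and leave. The controls who remain look healthier than the control arm as randomised, and the benefit is understated. If the product raises enzymes, the same process understates the harm. Adjusting for Day 0 recovers only part of the loss, because the exit depends on a later value.

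**Working it through.** **1. The protocol's own figure.** Section 13.2 fixes "significance of probability in one-tailed test will be taken to be 2.5"%, and says "the statistical power level will be chosen to be 90"%, with 40 per group. Section 13.1 says "All statistical tests will be two-sided and statistical significance level alpha will be set at 0.05 for the analysis". One-sided 2.5% and two-sided 5% share the same critical value, so these agree. No difference or SD is given, so 40 per group cannot be reproduced. The standardised difference it implies is

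d = √(2/40) × (1.960 + 1.282) = 0.2236 × 3.242 = 0.725.

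This only sets a scale. I use a true final difference of -0.7 SD.

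**2. Assumptions (none is in the protocol).**
- Values are normal with SD 1 and control mean 0.
- Three visits (0/1/2 months): arm effects 0, -0.4, -0.7 SD. Four visits (0/2/4/6 months): 0, -0.25, -0.5, -0.7 SD.
- Correlation ρ is 0.6 or 0.8 between all visits. For four visits, a correlation of 0.8 that decays with distance is added.
- A subject leaves once an intermediate value exceeds c = 1.0 or 1.5 SD, with the same c in both arms.

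**3. Closed form for one intermediate visit.** Let λ(x) = φ(x)/Φ(x). Among those with an intermediate value below c, the final mean is -ρλ(c) in controls and -0.7 - ρλ(c + 0.4) in the active arm. Hence

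difference in those remaining = -0.7 + ρ[λ(c) - λ(c + 0.4)].

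- c = 1.0: λ(1.0) = 0.2420/0.8413 = 0.2876; λ(1.4) = 0.1497/0.9192 = 0.1629; gap 0.1247. Loss is 15.9% of controls and 8.1% of actives.
  - ρ = 0.6: -0.7 + 0.075 = -0.625 (10.7% too small).
  - ρ = 0.8: -0.7 + 0.100 = -0.600 (14.3%).
- c = 1.5: λ(1.5) = 0.1295/0.9332 = 0.1388; λ(1.9) = 0.0656/0.9713 = 0.0676; gap 0.0712. Loss is 6.7% and 2.9%.
  - ρ = 0.6: -0.7 + 0.043 = -0.657 (6.1%).
  - ρ = 0.8: -0.7 + 0.057 = -0.643 (8.1%).

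**4. All settings.** I simulated 1,000,000 subjects per arm in each setting. The longitudinal column uses every observed visit by sequential regression.

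| Visits | Correlation | c | Final-visit difference | Day 0-adjusted | Longitudinal |
|---|---|---|---|---|---|
| 3 | 0.6 | 1.0 | -0.63 | -0.67 | -0.70 |
| 3 | 0.6 | 1.5 | -0.66 | -0.68 | -0.70 |
| 3 | 0.8 | 1.0 | -0.60 | -0.68 | -0.70 |
| 3 | 0.8 | 1.5 | -0.64 | -0.69 | -0.70 |
| 4 | 0.6 | 1.0 | -0.60 | -0.65 | -0.70 |
| 4 | 0.6 | 1.5 | -0.64 | -0.68 | -0.70 |
| 4 | 0.8 | 1.0 | -0.58 | -0.67 | -0.70 |
| 4 | 0.8 | 1.5 | -0.63 | -0.68 | -0.70 |
| 4 | 0.8, decaying | 1.0 | -0.59 | -0.63 | -0.70 |
| 4 | 0.8, decaying | 1.5 | -0.63 | -0.66 | -0.70 |

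Before rounding, dilution runs from 6.1% to 16.8%, and from 1.9% to 10.2% after Day 0 adjustment.

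**5. When there is no bias.** With no true effect and a common c, the bracket in step 3 is λ(c) - λ(c) = 0. With random exit, even at 10% in one arm and 30% in the other, the difference in those remaining equals the true one.

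**6. Replacement.** The formula in step 3 contains no sample size. A replacement under the same exit rule finishes only if the intermediate value is also below c. The finishers therefore keep the same truncated distribution: the count is restored and the dilution stays.

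**The case against.** **Section 13.1 does not say that mid-point values are thrown away.** This is correct. It may mean a test at each visit, in which case those values are used at their own visit. Analysis sets and missing-data rules may sit in an analysis plan that is not shown, and their absence is no fault here. What stands is narrower: none of the tests that the protocol names can carry a departed subject's mid-point value into the final-visit comparison.

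**A reader might infer that the final result is biased as a matter of course, or that false positives follow.** The documents do not support either. Bias needs exit related to outcome. Under one cut-off for both arms it shrinks a real effect and creates none. A check of the Wilcoxon test in those remaining, with no true effect, rejected 4% to 6% of the time. A false difference would need opposite reasons for leaving in the two arms. Section 12.2 applies one rule to both.

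**The exit rule is assumed.** No document gives a limit in SD units. Enrolment itself rests on laboratory evidence of the disease, and at c = 1.0 about 16% of subjects (1 - 0.8413) would already exceed the limit at Day 0. Section 12.1 counts an abnormal finding as an adverse event only with symptoms or a need for further work-up or treatment, whereas 12.2 withdraws for any abnormal finding. The two passages need reconciling. All this makes the size uncertain but not the direction.

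**The longitudinal estimate is accurate because exit was built to depend on measured values.** This is fair. Exits for rash, nausea, dyspepsia, poor adherence or request may not be explained by enzymes or lipids.

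**The gain is small.** After Day 0 adjustment the bias is at most about 0.07 SD, against standard errors of 0.15 to 0.22 at 40 per arm. This also stands and limits the weight of the point.

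**The root is withdrawal and replacement after randomisation.** That is largely true, and it affects imaging too. It does not make the single-visit test a good choice for data already collected.

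**Conclusion.** The point holds in a limited, conditional form. For enzymes and lipids, the protocol combines a withdrawal rule that acts on laboratory results with tests that ignore the results behind the exit. If exit depends on those values and the product has a real effect, the final-visit difference can be diluted by about 6% to 17%, or about 2% to 10% with Day 0 adjustment. These figures assume a true difference of -0.7 SD, correlation of 0.6 to 0.8 and a common cut-off of 1.0 to 1.5 SD. With random exit, or with no true effect under a common cut-off, the bias is zero.

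The point concerns secondary endpoints only. Section 7.4.2 schedules tomography at Day 0 and the end, so there is no scheduled mid-point image for a longitudinal model to use. Section 11 does mention liver size at an intermediate point, which does not match that schedule. The change is worth making because it is cheap, not because the trial's main conclusion turns on it.

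**What to change.** In section 13.1, make the main analysis of each enzyme and lipid a mixed model for repeated measures.

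- **Subjects:** everyone as randomised with any post-baseline value. Keep the data of withdrawn subjects up to exit, and do not let replacements stand in for them.
- **Terms:** arm, visit, arm-by-visit, Day 0 value and Day 0-by-visit.
- **Form:** log scale for skewed analytes, unstructured covariance, and a small-sample degrees-of-freedom correction where the software allows. Section 13.1 names Stata SE 12.1, so check this first. It matters most if the summary's 20 per group applies and not the 40 per group of section 13.2.
- **Result:** the arm difference at the final visit with its 95% confidence interval. The question stays the end-of-treatment one and does not become an average over visits.
- **Sensitivity:** keep the Wilcoxon test at the final visit.

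Reconcile the summary's 0/1/2-month visits with the 0/2/4/6-month visits of section 7.4.2, so that the final visit is defined.

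**Cost:** new wording and one model per analyte, on data already collected. The model relies on approximate normality and on exits being explained by measured values, which may fail for exits due to symptoms, adherence or request. It does nothing for the imaging endpoint.
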